10.5.4. Pharmacokinetics

PK Parameters

• If one or more non-quantifiable (NQ) values occur in a profile before the first measurable concentration, they will be assigned a value of zero concentration. For linear plots, zero concentration value(s) before the first measurable concentration will be included in the plot. For log-linear plots, zero concentration value(s) before the first measurable concentration will be assigned a missing value.• If a single NQ value occurs between measurable concentrations in a profile, the NQ should generally be set to missing in the derivation of pharmacokinetic parameters, statistical analysis, and the individual subject plots.• If two or more NQ values occur in succession between measurable concentrations, the profile will be deemed to have terminated at the last measurable concentration prior to these NQs. For the purpose of individual subject plots, these NQs will be set to 0, and the subsequent measurable concentrations will be retained. For the derivation of pharmacokinetic parameters, these NQs and any subsequent measurable concentrations will be set to missing.• NQs which occur after the last measurable concentration will be omitted (set to missing) in the derivation of pharmacokinetic parameters and from the individual subject plots.• Individual's PK parameters reported as 'NC' (Not Calculable) or 'ND' (Not Determined) will be included in listings but omitted (set to missing) from figures, summaries and statistical analyses.

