AUC(0-t) (h*ng/mL)	Area under the concentration-time curve from zero time (pre-dose) to the time of the last quantifiable concentration (AUC(0-t)) will be calculated by a combination of linear and logarithmic trapezoidal methods. The linear trapezoidal method will be employed for all incremental trapezoids arising from increasing concentrations and the logarithmic trapezoidal method will be used for those arising from decreasing concentrations (i.e., Linear Up/Log Down calculation method in Phoenix WinNonlin Professional).
AUC(0-inf) (h*ng/mL)	Area under the concentration-time curve from zero time (pre-dose) extrapolated to infinite time (AUC(0-inf)) will be calculated as follows: $\text{AUC}(0-\text{inf}) = \text{AUC}(0-t) + Ct / \lambda_z$
Cmax (ng/mL)	Maximum observed concentration will be obtained directly from the concentration-time data.
Tmax (h)	Time to first occurrence of Cmax will be obtained directly from the concentration-time data.
t1/2 (h)	Terminal phase half-life will be calculated as follows: $t_{1/2} = \ln 2 / \lambda_z$
tlag (h)	Lag time before observation of drug concentrations in sampled matrix.

Parameter	Parameter Description
tlast (h)	The time of the last measurable (positive) concentration.
%AUCex (%)	The area under the curve (AUC) from the last predicted non-zero concentration value to infinity as a percentage of the area under the curve extrapolated to infinity.
lambda_z (/h)	The first order rate constant associated with the terminal (log-linear) portion of the curve.
lambda_z_lower (h)	The lower limit on time for values to be included in the calculation of Lambda z.
lambda_z_upper (h)	The upper limit on time for values to be included in the calculation of Lambda z.
#pts	The number of time points used in computing Lambda z.
R2	The goodness of fit statistic for the terminal elimination phase.

NOTES:

- Additional parameters may be included as required.
- Lambda_z is the terminal phase rate constant.
- Ct is the last observed quantifiable concentration.

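### The rule that two consecutive non-quantifiable values end a profile is not limited to the terminal phase, so in an uncommon early pattern it discards the true peak

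*SAP*

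**What the plan says.** SAP 10.5.4 (Appendix 5) sets out how NQ concentrations are treated. The wording is the same in the initial RAP and in Amendment 1.

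- **Leading NQs.** "If one or more non-quantifiable (NQ) values occur in a profile before the first measurable concentration, they will be assigned a value of zero concentration".
- **A single embedded NQ.** "the NQ should generally be set to missing in the derivation of pharmacokinetic parameters". The word for usual practice leaves some discretion.
- **Two or more embedded NQs.** "If two or more NQ values occur in succession between measurable concentrations, the profile will be deemed to have terminated at the last measurable concentration" that precedes them. The rule continues: "For the derivation of pharmacokinetic parameters, these NQs and any subsequent measurable concentrations will be set to missing". There is no softening word and no reference to the peak or the terminal phase. The later concentrations are kept only for the individual plots.
- **Parameters reported as not calculable or not determined.** These "will be included in listings but omitted (set to missing) from figures, summaries and statistical analyses". No criterion says that a profile cut short by the NQ rule must be reported that way.

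SAP 8.3.1, Table 7, says of Cmax: "Maximum observed concentration will be obtained directly from the concentration-time data". AUC(0-t) runs to the last quantifiable value. Neither needs a terminal slope. After log transformation, these two parameters are the ones modelled in SAP 8.3.3.1 (dose proportionality) and 8.3.3.2 (food effect).

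**The concern.** Ending a profile at a run of NQs is sensible in the tail, where an odd late value should not extend the AUC. Before the peak it does harm.

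The schedule has four samples before 1 h (pre-dose, 0.25, 0.5 and 0.75 h), and lag time is a planned parameter, so some early samples may well be NQ. The leading-NQ rule protects them only until the first measurable value. If one isolated early value is quantified, the lag samples after it become embedded NQs. Two in a row end the profile before absorption has begun.

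AUC(0-inf) and half-life then cannot be derived, nor can AUC(0-24), because all three need a terminal slope that the truncated profile cannot supply. Cmax and AUC(0-t) are still computable from what remains, and they feed the main PK models. With 12 subjects per dose in Part 1 and 16 in Part 2, one value wrong by several log units carries visible weight.

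**Working it through.** **Plan's own precision (Protocol 10.1.1, Part 2).** Inputs: CVw 44.7%, n = 16, 90% CI.
- Log-scale variance: s² = ln(1 + 0.447²) = 0.1822, so s = 0.4268.
- Half-width = t(0.95, 14 df) × s × √(2/16) = 1.761 × 0.4268 × 0.3536 = 0.266.
- CI at a ratio of 1: exp(±0.266) = (0.77, 1.30), which matches the protocol.

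**The rule applied literally.** Assumed profile: peak 863 ng/mL, lag 0.8 h, planned sampling times. The limit of quantification is not stated; 1 to 10 ng/mL is assumed, with the stray value at 1.2 times the limit.

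| Stray value at | Cmax as written (ng/mL) | AUC(0-t) as written (h*ng/mL) | With the rule limited to after the peak |
|---|---|---|---|
| 0.25 h, then NQ at 0.5 and 0.75 h | 1.2 to 12 | 0.15 to 1.5 | Cmax 863; AUC(0-t) about 5,200 to 5,500 |
| Pre-dose, then NQ at 0.25 and 0.5 h | 1.2 to 12 | 0 (log undefined) | Cmax 863; AUC(0-t) about 5,200 to 5,500 |

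**Effect on the Part 2 ratio.** Assumptions: true 50 mg Cmax 0.863 and AUC 7.248 (Protocol 5.5; units not shown, read as ug/mL and h*ug/mL, so 863 ng/mL and 7,248 h*ng/mL), and a stray value of 5 ng/mL at 0.25 h. In the balanced crossover each subject carries weight 1/16 in the log ratio.
- Cmax: ln(5/863) = −5.151, and −5.151/16 = −0.322. The factor is exp(−0.322) = 0.72 if the fasted profile is hit, or 1/0.72 = 1.38 if the fed profile is hit.
- AUC(0-t): linear trapezoid 0.5 × 5 × 0.25 = 0.625. ln(0.625/7248) = −9.358, and −9.358/16 = −0.585. The factor is 0.56 (fasted) or 1.8 (fed).
- For stray values of 1 to 50 ng/mL, the Cmax factor is 0.66 to 0.84 (fasted).

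**Effect on precision (Cmax, 5 ng/mL, true ratio 1).**
- The outlier adds about 5.151² × (1 − 1/8) = 23.2 to the sum of squares of the within-subject differences.
- Variance of a difference: 2 × 0.1822 + 23.2/14 = 2.02. Standard error of the log ratio: √(2.02/16) = 0.356.
- Half-width: 1.761 × 0.356 = 0.626. The 90% CI becomes about (0.39, 1.36) around 0.72 (fasted), or (0.74, 2.58) around 1.38 (fed).
- Estimated CVw: √(exp(2.02/2) − 1), about 130% against the planned 44.7%.

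A simulation of the same design with one fed profile hit, and stray values of 1.2 to 12 ng/mL, agrees. The median fasted/fed ratio is 1.51 down to 1.30 for Cmax, and 1.97 down to 1.69 for AUC(0-t).

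**Part 1.** A slope shift of very roughly 0.1 to 0.4 is possible, but this is indicative only. It assumes a within-subject CV of 20% and a power model without the period term that the text of SAP 8.3.3.1 adds. Each active dose is given in only one period, so with that term no slope is estimable.

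**Carry-over as a cause.** The washout is at least 168 h and the half-life 11 to 12 h (Protocol 5.1 and 5.4). That is 14 to 15.3 half-lives, leaving about 0.02 to 0.05 ng/mL from 863 ng/mL. Carry-over is an unlikely source of a quantifiable value.

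**The case against.** The strongest reply is that the pattern is rare and would be noticed. Four readings that go further than the documents should be set aside.

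- **A reader might infer that fed dosing and early sampling make the rule misfire often.** They do not. Ordinary lag NQs precede the first measurable value and are set to zero. An isolated quantified value must come first, and the documents give no frequency, no expected lag and no limit of quantification.
- **A reader might infer that both parameters always enter the models near zero.** That holds only for a post-dose stray value. A pre-dose one gives AUC(0-t) = 0, which has no logarithm and drops out.
- **A reader might infer that the food-effect ratio would fall.** SAP 8.3.3.2 reports fasted/fed, so an affected fed profile raises it.
- **A reader might infer that a wrong number would pass silently into the report.** The individual plots would show a full curve beside a near-zero Cmax. Parameters are derived under clinical pharmacology oversight where the data allow, and data are reviewed before freeze. The guidance document cited in SAP 10.4.4 for NQ values in concentration summaries is not among the documents and might bear on this.

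These points limit likelihood and certainty. They do not supply a written safeguard. Overriding an explicit rule after seeing the data would be an unplanned decision, which a prespecified NQ rule is meant to avoid. The study estimates rather than tests, so no error rate is at stake, but the estimates are its main PK output.

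**Conclusion.** The point holds as a defect in the rule, confined to an uncommon trigger: an isolated early quantified value, then two or more NQs, then real absorption. In that case SAP 10.5.4 as written discards the true peak, and no written criterion keeps the remaining Cmax out of the models, or AUC(0-t) when the stray value is post-dose.

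The sizes in the working are for one affected profile out of 16 and show leverage, not expected bias. They rest on the assumed concentration units and stray value. The Part 1 effect should not be quoted as a firm figure. The amendment is worth making because the consequence is large when it occurs and the change is small.

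**What to change.** Amend SAP 10.5.4 as follows.

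1. Apply the termination rule for two or more consecutive NQs only to NQs after the main peak of the profile.
2. For a run of two or more NQs before the peak, set them to zero and retain all later measurable concentrations.
3. Leave the single-NQ rule unchanged.
4. Query the isolated early value and flag it in the listings. It stays in the profile and can distort the lag time.

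The cost is a few lines of SAP text and one small burden: the peak must be identified before the rule is applied. That step needs a check that a spurious late value has not been taken as the peak, because that would switch the rule off in the tail, where it is needed.

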10.6. Appendix 6: Premature Withdrawals & Handling of Missing Data

10.6.1. Premature Withdrawals

Element	Reporting Detail
General	
 Subject study completion was defined as a participant has completed all periods of the study including the last visit or the last scheduled procedure (Follow-up) for each period as described in the protocol. Withdrawn subjects maybe replaced in the study. All available data from subjects who were withdrawn from the study will be listed and all available planned data will be included in summary tables and figures, unless otherwise specified.

10.6.2. Handling of Missing Data

Element	Reporting Detail
General	
 Missing data occurs when any requested data is not provided, leading to blank fields on the collection instrument: 
 These data will be indicated by the use of a "blank" in subject listing displays. Unless all data for a specific visit are missing in which case the data is excluded from the table. Answers such as "Not applicable" and "Not evaluable" are not considered to be missing data and should be displayed as such.

10.6.3. Handling of Partial Dates

Element	Reporting Detail
Concomitant Medications	
 Partial dates for any concomitant medications recorded in the CRF will be imputed using the following convention: 
 If the partial date is a start date, a '01' will be used for the day and 'Jan' will be used for the month If the partial date is a stop date, a '28/29/30/31' will be used for the day (dependent on the month and year) and 'Dec' will be used for the month. The recorded partial date will be displayed in listings.

10.6.4. Handling of Missing Data for Statistical Analysis

Element	Reporting Detail
Imputation	
 No imputation will be performed for missing data

10.7. Appendix 7: Values of Potential Clinical Importance

10.7.1. Laboratory Values (Healthy Volunteers)

Haematology				
Laboratory Parameter	Units	Category	Clinical Concern Range	
			Low Flag (< x)	High Flag (>x)
Hematocrit	Ratio of 1	Male		0.54
		Female		0.54
		Δ from BL	↓0.075	
Hemoglobin	g/L	Male		180
		Female		180
		Δ from BL	↓25	
Lymphocytes	x10 ⁹ / L		0.8	
Neutrophil Count	x10 ⁹ / L		1.5	
Platelet Count	x10 ⁹ / L		100	550
White Blood Cell Count (WBC)	x10 ⁹ / L		3	20

Clinical Chemistry				
Laboratory Parameter	Units	Category	Clinical Concern Range	
			Low Flag (< x)	High Flag (>x)
Albumin	G/L		30	
Calcium	mmol/L		2	2.75
Creatinine	µmol/L	Δ from BL		↑ 44.2
Glucose	mmol/L		3	9
Phosphorus	mmol/L		0.8	1.6
Potassium	mmol/L		3	5.5
Sodium	mmol/L		130	150

Liver Function				
Test Analyte	Units	Category	Clinical Concern Range	
ALT/SGPT	U/L	High	≥ 2x ULN	
AST/SGOT	U/L	High	≥ 2x ULN	
AlkPhos	U/L	High	≥ 2x ULN	
T Bilirubin	µmol/L	High	≥ 1.5xULN	
T. Bilirubin + ALT	µmol/L U/L	High	1.5xULN T. Bilirubin + ≥ 2x ULN ALT	

10.7.2. ECG (Healthy Volunteers)

ECG Parameter	Units	Clinical Concern Range	
		Lower	Upper
Absolute			
Absolute QTc Interval	msec		> 450 [1]
Absolute PR Interval	msec	< 110 [1]	> 220 [1]
Absolute QRS Interval	msec	< 75 [1]	> 110 [1]
Change from Baseline			
Increase from Baseline QTc	msec	> 60 [1]	

NOTES:

1. Represent standard ECG values of PCI for HV studies

10.7.3. Vital Signs (Healthy Volunteers)

Vital Sign Parameter (Absolute)	Units	Clinical Concern Range	
		Lower	Upper
Systolic Blood Pressure	mmHg	< 85	> 160
Diastolic Blood Pressure	mmHg	< 45	> 100
Heart Rate	bpm	< 40	> 110

10.8. Appendix 8 - Abbreviations & Trade Marks

10.8.1. Abbreviations

Abbreviation	Description
AE	Adverse Event
A&R	Analysis and Reporting
AUC(0-24)	Area under the concentration-time curve from pre-dose to 24 hours
AUC(0-inf)	Area under the concentration-time curve from time zero (pre-dose) extrapolated to infinite time
AUC(0-t)	Area under the concentration-time curve from time zero (pre-dose) to last time of quantifiable concentration within a subject across all treatments
BMI	Body mass index
BP	Blood pressure
CI	Confidence Interval
Cmax	Maximum observed concentration
CSR	Clinical Study Report
CVb	Coefficient of variation (Between)
CVw	Coefficient of Variation (Within)
ECG	Electrocardiogram
eCRF	Electronic Case Report Form
GSK	GlaxoSmithKline
HR	Heart rate
hrs	Hours
IDSL	Integrated Data Standards Library
IMMS	International Modules Management System
LLN	Lower Limit of Normal
LLQ	Lower Limit of Quantification
MedDRA	Medical Dictionary for Regulatory Activities
MG	Milligrams
msec	Milliseconds
PDMP	Protocol Deviation Management Plan
PK	Pharmacokinetic
QC	Quality Control
QTcF	Frederica's QT Interval Corrected for Heart Rate
RAP	Reporting and Analysis Plan
SAC	Statistical Analysis Complete
SAE	Serious Adverse Event(s)
SAS	Statistical Analysis Software
SD	Standard Deviation
ULN	Upper Limit of Normal
SOP	Standard Operation Procedure
t1/2	Terminal half-life
Tmax	Time to maximum observed blood drug concentration
TFL	Tables, Figures & Listings

10.8.2. Trademarks

Trademarks of the GlaxoSmithKline Group of Companies	Trademarks not owned by the GlaxoSmithKline Group of Companies
None	SAS
	WinNonlin

10.9. Appendix 9: List of Data Displays

10.9.1. Data Display Numbering

The following numbering will be applied for RAP generated displays:

Section	Tables	Figures
Study Population	1.1 to 1.14	N/A
Safety	2.1 to 2.34	N/A
Pharmacokinetic	3.1 to 3.8	3.1 to 3.10
Section	Listings	
ICH Listings	1 to 71	
Other Listings	N/A	

10.9.2. Mock Example Referencing

Non IDSL specifications will be referenced as indicated and if required an example mock-up displays provided in Appendix 10: Example Mock Shells for Data Displays.

Section	Figure	Table	Listing
Study Population	POP_Fn	POP_Tn	POP_Ln
Safety	SAFE_Fn	SAFE_Tn	SAFE_Ln
Pharmacokinetic	PK_Fn	PK_Tn	PK_Ln

NOTES:

- Indicate display is Non-Standard in the 'IDSL/TST ID / Example Shell' or 'Programming Notes' column.

10.9.3. Deliverable [Priority]

Delivery [Priority] ^[1]	Description
PR [1]	Primary Report (Part 1 only)
SAC [2]	Statistical Analysis Complete

NOTES:

- Indicates priority (i.e. order) in which displays will be generated for the reporting effort.

10.9.4. Study Population Tables

Study Population Tables					
No.	Population	IDSL / TST ID / Example Shell	Title	Programming Notes	Deliverable [Priority]
Subject Disposition					
1.1.	Safety	CP_ES1	Summary of Subject Disposition (Part 1)	Completed or withdrawn and the reason for withdrawal.	PR [1]
1.2.	Safety	ES4	Summary of Subject Disposition at each period (Part 1)	Completed or withdrawn at each period.	PR [1]
1.3.	Safety	CP_ES1	Summary of Subject Disposition (Part 2)	Completed or withdrawn and the reason for withdrawal.	SAC [2]
1.4.	Screened	ES6	Summary of Screening Status and Reasons for Screen Failure	The number (%) of Randomized or screening failure subjects as the screening status, and the reason for screening failure.	SAC [2]
Protocol Deviation					
1.5.	Safety	DV1	Summary of Important Protocol Deviations (Part 1)	Data is from DV1 dataset.	PR [1]
1.6.	Safety	DV1	Summary of Important Protocol Deviations (Part 2)	Data is from DV1 dataset.	SAC [2]
Population Analysed					
1.7.	Safety	SP1	Summary of Study Populations (Part 1)	Only PK population is summarized.	PR [1]
1.8.	Safety	SP1	Summary of Study Populations (Part 2)	Only PK population is summarized.	SAC [2]
Demographic and Baseline Characteristics					
1.9.	Safety	DM3	Summary of Demographic Characteristics (Part 1)		PR [1]
1.10.	Safety	DM3	Summary of Demographic Characteristics (Part 2)		SAC [2]
1.11.	Screened	DM11	Summary of Age Ranges (Part 1)	<=17 years, 18-64 years, 65-84 years, >=85 years	PR [1]
1.12.	Screened	DM11	Summary of Age Ranges (Part 2)	<=17 years, 18-64 years, 65-84 years, >=85 years	SAC [2]

CONFIDENTIAL

206817

Study Population Tables					
No.	Population	IDSL / TST ID / Example Shell	Title	Programming Notes	Deliverable [Priority]
1.13.	Safety	DM5	Summary of Race and Racial Combinations (Part 1)		PR [1]
1.14.	Safety	DM5	Summary of Race and Racial Combinations (Part 2)		SAC [2]

10.9.5. Safety Tables

Safety: Tables					
No.	Population	IDSL / TST ID / Example Shell	Title	Programming Notes	Deliverable [Priority]
Adverse Events (AEs)					
2.1.	Safety	AE1	Summary of All Adverse Events by System Organ Class and Preferred Term (Part 1)		PR [1]
2.2.	Safety	AE5A	Summary of All Adverse Events by Maximum Intensity (Part 1)		PR [1]
2.3.	Safety	AE1	Summary All Drug-Related Adverse Events by System Organ Class and Preferred Term (Part 1)		PR [1]
2.4.	Safety	AE5A	Summary All Drug-Related Adverse Events by Maximum Intensity (Part 1)		PR [1]
2.5.	Safety	AE1	Summary of All Adverse Events by System Organ Class and Preferred Term (Part 2)		SAC [2]
2.6.	Safety	AE5A	Summary of All Adverse Events by Maximum Intensity (Part 2)		SAC [2]
2.7.	Safety	AE1	Summary All Drug-Related Adverse Events by System Organ Class and Preferred Term (Part 2)		SAC [2]
2.8.	Safety	AE5A	Summary All Drug-Related Adverse Events by Maximum Intensity (Part 2)		SAC [2]
Laboratory: Chemistry					
2.9.	Safety	LB1	Summary of Chemistry (Part 1)		PR [1]
2.10.	Safety	LB1	Summary of Chemistry Changes from Baseline (Part 1)		PR [1]
2.11.	Safety	LB4	Summary of Chemistry Data Shifts from Baseline with Respect to the Normal Range (Part 1)		PR [1]
2.12.	Safety	LB1	Summary of Chemistry (Part 2)		SAC [2]
2.13.	Safety	LB1	Summary of Chemistry Changes from Baseline (Part 2)		SAC [2]

Safety: Tables					
No.	Population	IDSL / TST ID / Example Shell	Title	Programming Notes	Deliverable [Priority]
2.14.	Safety	LB4	Summary of Chemistry Data Shifts from Baseline with Respect to the Normal Range (Part 2)		SAC [2]
Laboratory: Hematology					
2.15.	Safety	LB1	Summary of Hematology (Part 1)		PR [1]
2.16.	Safety	LB1	Summary of Hematology Changes from Baseline (Part 1)		PR [1]
2.17.	Safety	LB4	Summary of Hematology Data Shifts from Baseline with Respect to the Normal Range (Part 1)		PR [1]
2.18.	Safety	LB1	Summary of Hematology (Part 2)		SAC [2]
2.19.	Safety	LB1	Summary of Hematology Changes from Baseline (Part 2)		SAC [2]
2.20.	Safety	LB4	Summary of Hematology Data Shifts from Baseline with Respect to the Normal Range (Part 2)		SAC [2]
Laboratory: Urinalysis					
2.21.	Safety	UR3b	Summary of Urinalysis Data (Glucose, Protein, Blood, Ketones, Bilirubin, Urobilinogen) (Part 1)		PR [1]
2.22.	Safety	LB1	Summary of Urinalysis Data (Specific Gravity and pH) (Part 1)		PR [1]
2.23.	Safety	UR3b	Summary of Urinalysis Data (Glucose, Protein, Blood, Ketones, Bilirubin, Urobilinogen) (Part 2)		SAC [2]
2.24.	Safety	LB1	Summary of Urinalysis Data (Specific Gravity and pH) (Part 2)		SAC [2]
ECG					
2.25.	Safety	EG1	Summary of ECG Findings (Part 1)		PR [1]
2.26.	Safety	EG2	Summary of ECG Value (Part 1)		PR [1]
2.27.	Safety	EG2	Summary of Change from Baseline in ECG Values (Part 1)		PR [1]
2.28.	Safety	EG1	Summary of ECG Findings (Part 2)		SAC [2]

CONFIDENTIAL

206817

Safety: Tables					
No.	Population	IDSL / TST ID / Example Shell	Title	Programming Notes	Deliverable [Priority]
2.29.	Safety	EG2	Summary of ECG Value (Part 2)		SAC [2]
2.30.	Safety	EG2	Summary of Change from Baseline in ECG Values by Visit (Part 2)		SAC [2]
Vital Signs					
2.31.	Safety	VS1	Summary of Vital Signs (Part 1)		PR [1]
2.32.	Safety	VS1	Summary of Change from Baseline in Vital Signs (Part 1)		PR [1]
2.33.	Safety	VS1	Summary of Vital Signs (Part 2)		SAC [2]
2.34.	Safety	VS1	Summary of Change from Baseline in Vital Signs (Part 2)		SAC [2]

10.9.6. Pharmacokinetic Tables

Pharmacokinetic: Tables					
No.	Population	IDSL / TST ID / Example Shell	Title	Programming Notes	Deliverable [Priority]
Part 1					
3.1.	PK	PK01: pkct1	Summary of GSK1325756 Blood Concentration (ng/mL) (Part 1)		PR [1]
3.2.	PK	PK03: pkpt1	Summary of GSK1325756 Pharmacokinetic Parameters (non-transformed) (Part 1)		PR [1]
3.3.	PK	PK05: pkpt3	Summary of GSK1325756 Pharmacokinetic Parameters (loge-transformed) (Part 1)		PR [1]
3.4.	PK	Study Specific (PK_T1)	Analysis of Power Model Analysis for GSK1325756 Dose Proportionality of Pharmacokinetic Parameters (AUC(0-t), Cmax) (Part 1)	Parameter, Effect, n, Point estimate of Slope, SE, 90% CI	PR [1]
Part 2					
3.5.	PK	PK01: pkct1	Summary of GSK1325756 Blood Concentration (ng/mL) (Part 2)		SAC [2]
3.6.	PK	PK03: pkpt1	Summary of GSK1325756 Pharmacokinetic Parameters (non-transformed) (Part 2)		SAC [2]
3.7.	PK	PK05: pkpt3	Summary of GSK1325756 Pharmacokinetic Parameters (loge-transformed) (Part 2)		SAC [2]
3.8.	PK	Study Specific (PK_T2)	Analysis of food effect for Pharmacokinetic Parameters (AUC(0-t), Cmax) (Part 2)	n, Geometric mean of Fasted and Fed, ratio (Fasted/Fed), 90% CI and CVw(%)	SAC [2]

